#### 3.5.4.2. Device Use Time

Subjects will receive their study device (Accu-Chek® Solo micropump system, MDI, or OmniPod®) at Visit 2. Additionally, as described above, study subjects randomized to arms B and C will utilize two devices at the day of Visit 4. Consequently, for all analyses utilizing the number of days a given device is used, use time will be calculated starting at Visit 2. For subjects randomized to treatment arms B (MDI) and C (OmniPod), the day of Visit 4 will be counted for

both, that is for the randomized device and for the Accu-Chek® Solo micropump system. For subjects in treatment group A, the Visit 4 day will however only be counted once.

### 3.5.5. Coding of Adverse Events and Medical History

Adverse event and medical history terms are coded using the Medical Dictionary for Regulatory Activities (MedDRA) terminology version in effect at the time the database is closed. MedDRA term level (LLT, PT, and SOC) are utilized depending on the particular needs of a given analysis. What term level will be used will be defined with the analysis definition.

Certain medical conditions, e.g. hyperglycaemia and ketonuria have completely different MedDRA codings, however they may be caused by identical reasons, e.g., lack of insulin. Medical Safety may therefore request pooling of such events. If this is applied, it will be explained as part of the respective analysis.

### 3.5.6. Coding of medications

Previous and concomitant medications are coded using the WHODrug dictionary. A semi-automatic coder built into the Marvin eCRF system is used for coding and the results will be extracted to SAS files for further analysis.

## 4. Variables for Analysis

In this section, data sources whose origin or initial preparation is not obvious are explained. Details about the actual analysis are provided in section 6.

Wherever text in languages other than English has been entered in sections relevant for analysis (e.g., in questionnaires), these texts will be translated into English and the English translation will be provided in listings etc.

### 4.1. Data for Primary Analysis

Change in treatment satisfaction is assessed by the answers to the change part questions (“How has it changed compared to your treatment before the study?”) of the Technology Questionnaire (DTQ). Each of these answers has a score between 1 (much worse) and 5 (much better). The sum of all 30 individual answers will be calculated for each subject/visit combination and will be used for analysis. Missing values will be imputed as described in section 3.4.1.

Answers entered in the status part (“Is this a problem now?”) of this questionnaire at visit 1 will be used as covariate.

## 4.2. Data for other Analyses

### 4.2.1. Questionnaires

#### 4.2.1.1. DTQ Questionnaire Change and Status Parts

As described section 4.1, the DTQ questionnaire consists of a change part in which subjects are asked for changes in their treatment satisfaction and of a status part, in which they are asked for their current rating. The change score (with V1 status score as covariate) will be used to analyze change compared to pre study status, while the differences between V4 and V5 (e.g., for subjects changing from MDI or the mylife™ OmniPod® therapy system to the Accu-Chek® Solo micropump system) will be calculated based on the respective “now” scores.

#### 4.2.1.2. DTQ Questionnaire Part 2 (User Friendliness)

Part 2 of the DTQ questionnaire consists of individual sections with 9 questions each for blood glucose meters, insulin pumps, and CMG devices. Main focus of part 2 questions is user-friendliness. Individual scores range from 1 (Terrible) to 5 (Excellent). Thus the resulting sum score ranges between 9 and 45 for each type of device. For all sections, higher scores denote a better user-friendliness.

Missing individual answers will be handled in accordance to the described handling for part 1. If three or less answers are missing in a given section, the total section score will be calculated as nine times the mean of the all answers provided. If more answers are missing, the entire section will be considered as missing and the LOCF procedure defined for DTQ will be applied.

#### 4.2.1.3. PAID-5 Questionnaire (Emotional Distress)

The PAID-5 questionnaire consists of 5 questions with answers ranging from 0 (Not a problem) to 4 (Serious problem). The total score will be calculated as the sum of the individual questions, resulting in a number between 0 and 20 where lower scores are better.

Missing individual answers will be treated in accordance to the procedure described for DTQ. If one answer is missing, the mean of the answers provided will be used to calculate the total

sum, otherwise the questionnaire will be treated as missing and the LOCF procedure will be applied.

#### **4.2.1.4. Roche Questionnaire**

The Roche questionnaire consists of 28 questions covering six areas, namely “Diabetes manager” (5 questions), “Pump” (4 questions), “Changeover” (4 questions), “Adhesive pad” (3 questions), “Overall system” (7 questions), and “Miscellaneous” (5 questions). Answers in the first five of these areas range from 4 (Agree) to 0 (Disagree) where higher scores are better. The “Miscellaneous” area consists of 5 free text answers. Total area scores from the first five areas will be calculated as the sum of scores in this area while the total questionnaire score will be calculated as the sum of all scores of the questionnaire. The total score will therefore be between 0 and 92. The free-text answers in the “Miscellaneous” section will only be listed but not further analyzed.

Missing individual answers will be treated in accordance to the procedure described for the DTQ. If more than one answer is missing for an individual section, this section will be treated as missing. For completely missing questionnaires, the LOCF procedure described earlier will be applied. Otherwise, sum scores will be calculated as described for DTQ.

#### **4.2.1.5. Examination of Insertion Sites**

Subjects are asked to assess five different properties describing potential problems at the pump insertion site, namely “itching”, “redness”, “swelling”, “heat”, and “pain”. Each of these questions can be answered with one of four alternatives, “None”, “Minor”, “Moderate”, and “Severe”.

#### **4.2.2. Blood Glucose Data**

Study subjects utilize various alternatives to collect blood glucose data during this study. The main distinctive feature is, whether collection is based on spot (BGM) or continuous (CGM) measuring. Differences within these two major classes are not of interest for this study.

Certain analyses are only meaningful for data originating from one of the two technologies, e.g., average number of SMBGs per day, while others may be utilized for both. The analysis will consider this by analyzing BGM and CGM data separately. Details are described in section 6.8.4.

### 4.2.3. Insulin Dosing

Insulin dosing information, i.e. insulin types, basal and bolus rates, and total insulin consumption will be taken from the entries in the eCRF. For pump users, more precise dosing information will additionally be extracted from the uploaded device data where possible. For analysis purposes, data taken from the eCRF and data acquired from device uploads will be used and listed separately.

## 5. Data Review

Before database closure, a Data Review Meeting (DRM) will be performed. In case there are open questions/discrepancies for a subject that cannot be solved via internal data review, a list with a description of the open issues will be evaluated case-by-case.

## 6. Statistical Analyses and Representation of Results

### 6.1. General

All analyses will be performed by SAS (Statistical Analysis Software), version 9.4. The analysis will be executed and checked according to SOP 04.04.50 V1.0 "Statistical Analysis of Clinical Trials".

Wherever appropriate, e.g., for demographics, descriptive analyses for the different treatment groups will be tabulated next to each other in the same row to allow for visual comparison. No statistical testing will however be performed unless specified explicitly in this document.

### 6.2. Analysis Populations

Primary population for all except safety relevant analyses is the FAS as described in section 2.10. Additionally, for completeness, the primary analysis will also be performed on the per protocol population. All safety relevant analyses will be performed on the SP.

#### 6.2.1. Distinction of Study Phases

As already described in 2.10, the study consists of two phases. To allow for easy distinction e.g., in listings, two variables, Arm and Trt are assigned to data acquired from each subject depending on the study phase and device assignment during data assessment.

| Arm Variable | Phase 1 (V1 - V4) |              | Phase 2 (V4 – V5) |              |
|--------------|-------------------|--------------|-------------------|--------------|
|              | Device            | Trt Variable | Device            | Trt Variable |
| A            | Solo              | A            | Solo              | A            |
| B            | MDI               | B            | Solo              | A            |
| C            | OmniPod           | C            | Solo              | A            |

Descriptive statistics for V5 data will both be calculated separately for each study arm and overall for all subjects.

### 6.3. Statistical Analysis Methods

The default summary statistics for continuous variables will be the number of observations (n), mean, standard deviation (SD), median, first and third quartile (Q1 and Q3), minimum (min), and maximum (max).

Apart from DTQ with its explicit change score, change from baseline will everywhere be evaluated by subtracting the baseline value from the value observed at the visit of interest. Whenever change scores will be listed or tabulated, the same statistics will also be presented for the baseline and visit values.

All summary statistics will be presented to one more decimal place than the raw value, except for the minimum and maximum values that will be presented with the same decimal precision as the raw value. Percentage values will be presented to one decimal place. Thus, percentages lower than 100% will be displayed as “XX.X”. E.g., a proportion of 0.655 will be presented as 65.5% where percent scores are given.

Percentages will be calculated using a denominator of all patients in a specified population or treatment group. The denominator will be specified in a footnote to the tables for clarification if necessary.

For qualitative variables, in general, the number (n) and percentage (%) of patients with non-missing data per category will be the default summary presentation, and where appropriate and present, the number of missing values as a “Missing” category.

#### **6.4. Presentation and Naming of Tables, Figures, and Listings**

Tables, figures, and listings will utilize a continuous numbering. First, tables starting with “Table 1”, then Figures starting with “Figure 1” and then listings. The orientation of the document will switch between portrait and landscape depending on space requirements. If a given table or listing does not fit on a page horizontally, the characters “a”, “b”, etc. will be added to the name and extra columns will be put into additional outputs, e.g., “Table 5a”, “Table 5b”, etc.

#### **6.5. Interim Analysis**

An interim analysis will be conducted when all patients have either passed visit 4 (End of parallel phase) or withdrawn from the study, i.e. when all data for performing the primary analysis and the majority of the secondary analyses are available. This will however be no typical interim analysis with possible adjustment of sample size etc. In this study, no changes on the study protocol nor on the study conduct will be made as a consequence of the results of this interim analysis.

#### **6.6. Analysis of Primary Endpoint DTQ**

The primary endpoint of this study is the change in DTQ part 1 as described in 2.5. A hierarchical procedure as described in section 2.7 will be applied. The comparison between Accu-Chek® Solo and mylife™ OmniPod® will only be performed, if the Null Hypothesis of no difference between Accu-Chek® Solo and MDI can be rejected.

The comparisons will be performed using an ANCOVA with the DTQ score as dependent variable and treatment arm, baseline DTQ score, and site as covariates. SAS proc GLM will be used for the analysis.

#### **6.7. Analyses of secondary endpoints for static variables**

##### **6.7.1. Disposition**

Disposition of subjects will be presented by means of:

- Enrolled subjects: All subjects having signed the Subject Informed Consent Form
- Screening failures: Subjects failing one or more inclusion or exclusion criteria
- Randomized subjects
- Withdrawn subjects:

Except for the number of screened subjects, percentages will be provided based on the number of eligible subjects in the respective group of interest. For screening failures, only those inclusion or exclusion criteria will be listed, that were decisive for the failure. For withdrawn subjects, the completion status and the reason for discontinuation will be listed.

### **6.7.2. Demographics**

The following demographic variables will be listed by subject and tabulated by treatment arm

- Sex
- Race
- Age
- Highest level of education
- Handedness
- Marital status
- Current employment

### **6.7.3. Baseline Characteristics**

The following characteristics will be collected at screening and/or baseline visit and will be listed by subject and tabulated by treatment arm:

- Height
- Weight
- BMI

#### 6.7.4. Diabetes History

The following diabetes history related properties will be listed by subject and tabulated by treatment arm.

- Duration of Diabetes
- Diabetes therapy at screening
- Start of diabetes therapy at screening
- Has CGM ever been used
- CGM use (weeks) during last 12 month
- Average daily SMBG frequency during last 3 months
- Previous use of a bolus calculator
- Type of basal insulin
- Type of bolus insulin

#### 6.8. Secondary Endpoints Analyzed by Visit

The following secondary endpoints will be analyzed by study arm and visit. Additionally, since subjects in treatment arms B and C will be switched to Solo micropump treatment after Visit 4, within treatment arm analyses will also be performed where applicable, i.e. analysis will be performed on Visit 4 versus Visit 5 data within each of these two study arms and for completeness, also for arm A.

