### 2.1 Study Design Overview

This is a multinational randomized, three arm interventional study. Subjects will be randomized to one of the following treatments:

- **Group A:** Accu-Chek® Solo micropump system for 39 weeks
- **Group B:** MDI for 26 weeks, then Accu-Chek® Solo micropump system for 13 weeks
- **Group C:** mylife™ OmniPod® for 26 weeks, then Accu-Chek® Solo micropump system for 13 weeks

Total duration is 40 weeks, during which all subjects switch from MDI to tubeless CSII at a time point determined by their allocated group. After 26 weeks, all subjects will use Accu-Chek® Solo micropump system.

In the case that mylife™ OmniPod® should not be commercially available in a country; no subjects will be randomized into Group C at the respective sites.

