### 11.6 Secondary Objective(s) Analysis

For subjects from groups B (starting with MDI) and C (starting with mylife™ OmniPod®), who will all use the Accu-Chek® Solo micropump after week 26, the change in DTQ score between week 26 and week 39 will be analyzed.

Additionally, the following parameters will be tested. More parameters may be specified in the statistical analysis plan (SAP). Both pairwise tests (Accu-Chek® Solo versus MDI and Accu-Chek® Solo versus mylife™ OmniPod®) and simultaneous analyses of all three treatment alternatives will be performed where applicable, e.g. using an Ancova with treatment arm as independent variable. Baseline adjustment will be performed where applicable. Details will be specified in the SAP.

- Psychological parameters that describe or affect therapy:
  - Treatment satisfaction with Accu-Chek® Solo system vs. mylife™ OmniPod®, measured by the difference in the Diabetes Technology Questionnaire (DTQ) change score after 26 weeks.
  - Diabetes-related Emotional Distress assessed by PAID-5.
  - Device satisfaction
  - Device and Treatment Preference
- Physical parameters that describe therapy changes or success:
  - HbA1c
  - Change in weight and BMI
  - Glycemic variability
- Therapy parameters that describe therapy changes or may affect the results
  - Indication for commencement of CSII
  - Type of insulin used
  - Total daily insulin dose (TDD)

- Total daily basal insulin dose (TBD)
- Average number of SMBGs per day
- Frequency of hypoglycemic events
- Frequency of hyperglycemia
- Frequency of consultations between scheduled visits, emergency and call center calls, hospitalizations and absenteeism from work/school
- Device specific parameters that may affect user acceptance
  - Number of pods/ infusion assemblies falling off prematurely
  - Average infusion assembly usage time
  - Number, type and intensity of skin reactions
- Parameters that may affect socio-economic acceptance
  - Insulin amount left in device at reservoir change / device discard
  - Amount of waste, inferred by total material consumption
- Subject withdrawal
  - It will be tested whether there is a bias in the fraction of subject withdrawal among the different treatment arms
- Descriptive evaluation:
  - Accu-Chek® Solo micropump system: Training Satisfaction

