## **6.13. Special Analytical Issues**

### **6.13.1. Treatment of incomplete or unmonitored data due to Covid-19 pandemic risk mitigation**

The Covid-19 pandemic during the final phase of this study may impact data collection in two different ways. Firstly, in order to avoid the risk of infection at the study sites, some of the subjects did not come to the site in person for the final study visit (V5); this visit was then

performed as a phone-call visit (virtual visit). And secondly, monitoring of some subject data was not possible due to unavailability of site staff.

Neither of these restrictions or changes has any impact on the primary study results, i.e., on analysis of the DTQ.

However the following data from V5 are expected to be missing for those subjects that completed V5 virtually: weight, HbA1c, pregnancy test, skin reaction assessment, device data upload, return of study material.

Missing data will be handled according to the description in section 3.4; no specific analysis pertaining to virtual visits will be performed.

The lack of monitoring however may result in wrong or missing entries in the eCRF. The monitoring status of all variables used for analyses will therefore be extracted from the eCRF and all variables, that have not been monitored, will be displayed underlined in all listings.

Additionally, all descriptive statistics and statistical tests based on data, that include data not monitored will be performed twice. Firstly, using the data as entered in the eCRF and secondly based on data generated by removing the data, that has not been monitored, and replacing it according to the missing value treatment described in section 3.4.

Differences in the statistics obtained using these two different approaches will illustrate the potential impact the data not monitored may have on study results.

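### The week-26 switch to Solo is assessed by Visit 4 versus Visit 5 changes within arms B and C, with no contrast against arm A, so it cannot be separated from effects that all arms share

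*SAP*

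**What the plan says.** Protocol 2.1 fixes one sequence per arm:

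- Arm A: "Accu-Chek® Solo micropump system for 39 weeks".
- Arm B: "MDI for 26 weeks, then Accu-Chek® Solo micropump system for 13 weeks".
- Arm C: OmniPod "for 26 weeks, then Accu-Chek® Solo micropump system for 13 weeks".

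No arm changes in the other direction.

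Protocol 11.6 opens with the switch. For groups B and C, "the change in DTQ score between week 26 and week 39 will be analyzed". Arm A is not mentioned in that sentence.

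SAP 6.8 adds within-arm analyses of Visit 4 against Visit 5. The reason it gives is the switch itself: "since subjects in treatment arms B and C will be switched to Solo micropump treatment after Visit 4". They are run "within each of these two study arms and for completeness, also for arm A".

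SAP 4.2.1.1 states that Visit 4 to Visit 5 differences, for example in subjects changing device, "will be calculated based on the respective “now” scores", meaning the DTQ status part. SAP 6.8.1.1 uses the primary ANCOVA for DTQ change scores and t-tests for all other DTQ comparisons, without saying whether these are paired or two-sample. SAP 6.1 rules out tests that the SAP does not explicitly specify.

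SAP 6.13.1 records that the pandemic fell in the final phase and that some Visit 5s were held by phone. It adds that "no specific analysis pertaining to virtual visits will be performed".

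**The concern.** A before-after difference within one arm estimates the effect of the switch only if nothing else moved the score over the same 13 weeks. Here several things could have: season and calendar time, the pandemic, a final visit by phone instead of at the site, and the approach of the end of the study. With a single order of treatments in each of B and C, the data from those arms alone cannot tell these apart from the change of device.

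Arm A is a randomised concurrent group that stays on Solo and follows the same visit schedule. It carries the information needed to remove whatever is common to the arms. The SAP gives it only its own before-after analysis. Separate results, such as a significant change in B and a non-significant one in A, do not test whether the two changes differ.

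At stake is the interpretation of the DTQ status-score change after the switch. A shared drift could give a significant change in B and C, in either direction, when the switch itself did nothing.

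**Working it through.** **The plan's own figure.** SAP 2.8: means 90 and 110, SD 30, two-sided alpha 0.05, 90% power, 49 per group. The normal approximation gives 2 × 30² × (1.960 + 1.282)² / 20² = 47.3, so 48. With the exact noncentral t, power is 89.8% at 48 and 90.4% at 49, so 49 reproduces. Dropout: 49 / 0.82 = 59.8, so 60. This calculation covers the primary comparison only. The documents give no sample size or power for the switch analysis.

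**Inputs for the illustration.**
- n = 49 per arm (SAP 2.8, after dropout).
- No switch effect (assumed).
- Drift common to all arms of 5 or 10 points (assumed; the documents give no value).
- SD of the Visit 4 to Visit 5 status-score change: 15 to 30 (assumed). The only SD in the documents is 30, and it is for the DTQ change score across subjects. If it also held for the status score, the SD of the difference would be 30 × √(2(1 − r)), with r the Visit 4 to Visit 5 correlation. An SD of 30 then corresponds to r = 0.5, and an SD of 15 to r = 0.875.

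**Within-arm test.** One-sample t on the difference, 48 degrees of freedom, critical value 2.011. The standard error is SD/√49 = SD/7 and the noncentrality is 7 × drift / SD.

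**Contrast with arm A.** The standard error is SD × √(2/49). A drift equal in both arms has expectation zero in the contrast.

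| SD of change | SE within arm | SE of contrast | P(within-arm p < 0.05), drift 5 | Drift 10 |
|---|---|---|---|---|
| 15 | 2.14 | 3.03 | 0.63 | 0.995 |
| 20 | 2.86 | 4.04 | 0.40 | 0.93 |
| 25 | 3.57 | 5.05 | 0.28 | 0.78 |
| 30 | 4.29 | 6.06 | 0.21 | 0.63 |

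Below the assumed range of correlations, at r = 0.3, the SD of change is 35.5 and the two probabilities are 0.16 and 0.49, still well above 0.05.

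**Check by simulation** (SD of change 30, n = 49, common drift 5, no switch effect): the within-arm test rejects in 20.9% of trials, the contrast with A in 5.1%.

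**What the contrast does and does not remove.** Set against the documents:
- Calendar time, the pandemic period and the end of the study reach all three arms over the same study weeks, so they cancel as far as their effect is the same in each arm. Phone visits cancel only if their share is similar across arms, which the documents do not report.
- Solo training at Visit 4 is for groups B and C only (protocol Schedule of Assessments and 7.9). It does not cancel.
- Arm A enters phase 2 with 26 more weeks on Solo than B and C. This does not cancel.
- Arm A subjects on a device without CE mark hand it back at Visit 4 (protocol 7.5), so a change of device version is possible. This does not cancel either.

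**The case against.** The strongest case on the other side is that the plan claims nothing for the switch. There is no hypothesis or success rule for it. The hypotheses in protocol 11.1 and SAP 2.6 concern the parallel randomised comparison. This stands: a reader might infer that the plan will read the Visit 4 to Visit 5 change as a Solo effect, but no section says so. What the documents show is that the analysis cannot separate the two.

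Other stronger readings also fail:
- The switch analysis comes first in protocol 11.6, but it is not among the secondary objectives in protocol 4.2 or SAP 2.1.
- It is not the only within-person comparison of Solo with MDI. The DTQ change part asks subjects to compare with their treatment before the study, and all came from MDI with no earlier pump use. Arm A's change score is already such a rating. For OmniPod there is no equivalent.
- Significance testing of the change is at issue essentially for the DTQ only. For PAID-5, HbA1c and most other endpoints, the SAP tabulates by-visit differences and specifies no Visit 4 to Visit 5 test.

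It can also be argued that the SAP leaves room for between-arm work. Protocol 11.6 foresees pairwise and three-arm analyses where applicable, the ANCOVA for DTQ change scores contains arm, the t-tests are not said to be paired, and Visit 5 statistics are given per arm. So a reader will have arm A's data. But room is not specification. An ANCOVA of Visit 5 change scores compares the sequences when everyone is on Solo; it does not estimate the change across the switch.

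The pandemic argument has a limit too: SAP 6.13.1 does not list questionnaires among the data expected to be missing at virtual visits, and it gives no count of such visits.

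Finally, the B-minus-A contrast equals the A-minus-B gap at Visit 4 less the same gap at Visit 5. If the arms converge on Solo, it largely restates the week-26 status-score comparison with more variance. That is true and limits what the analysis adds. It does not make the uncontrolled change a better estimate.

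**Conclusion.** The point holds for the DTQ status score. The switch is assessed by changes within B and C, arm A is analysed alongside and not as a control, and no contrast of changes is specified. Effects shared by all arms between weeks 26 and 39 therefore cannot be separated from the switch.

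The size is illustrative. With 49 per arm and no switch effect, a common drift of 5 points gives a significant within-arm result with probability 0.63 to 0.21 for an SD of change of 15 to 30, and a drift of 10 points with probability 0.995 to 0.63, against a nominal 0.05. Drift and SD are assumptions. Whether any drift occurred, and in which direction, cannot be learned from the documents.

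A reader might infer that the trial's main conclusion is at risk. It is not: the primary Solo versus MDI and Solo versus OmniPod comparisons are randomised, parallel and made at week 26. This is a worthwhile improvement to a secondary analysis.

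**What to change.** In SAP 6.8 and 6.8.1.1, for the DTQ status score:

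1. Make the main analysis of the switch the contrast of the Visit 4 to Visit 5 change, B minus A and C minus A, each with a 95% confidence interval, with the Visit 1 status score and site as covariates. The Visit 1 score is taken before randomisation. The Visit 4 score follows 26 weeks of different treatments, and adjusting for it would change the question.
2. Label the within-arm changes in A, B and C descriptive.
3. Repeat the contrasts without virtual Visit 5s, as a sensitivity analysis.
4. State in the report what does not cancel: Solo training at Visit 4 in B and C only, arm A's 26 extra weeks on Solo, and a possible change of device version in arm A at Visit 4.

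The cost is SAP wording and a few model runs on data already collected. Precision falls: the standard error is √2, about 1.4, times that of the within-arm change. At n = 49 and an SD of change of 30, the difference detectable with 90% power rises from 14.2 to 19.8 points, before any gain from the covariates.
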